9. PLANNED STATISTICAL METHODS

9.1 General Considerations

The statistical analysis and PK analysis will be performed by the sponsor or a designee. The detailed statistical analysis methods will be specified in a statistical analysis plan (SAP) and PK analysis plan according to this section of the study protocol. If analyses deviated from those outlined in the protocol, the reason for deviation from the protocol will be described in the SAP and PK analysis plan. The SAP and PK analysis plan will be finalized before scheduled unblinding.

Unless otherwise noted, continuous variables will be summarized by using the number of nonmissing observations, arithmetic mean, standard deviation, median, minimum, and maximum values as descriptive statistics; categorical variables will be summarized by using the frequency count and the percentage of patients in each category as descriptive statistics.

All statistical tests will be performed at the 0.05 significance level using 2-sided tests, except where otherwise noted. The primary endpoint will first be compared between the S-033188 and placebo groups for patients (primary analysis). Together with the primary efficacy analysis, a comparison between the S-033188 group and the oseltamivir group (secondary analysis) will be conducted in a hierarchical manner so as to maintain control of overall type I error. For Japan, control of overall type I error is not required for the secondary efficacy analysis of the primary endpoint. All patient study data will be presented in listings. In general, all tables will be presented by treatment group. Individual patient data will be presented by treatment and by patient. All analyses and tabulations will be performed by using both SAS[®] Version 9.2 or higher and WinNonlin[®] Version 6.2.1 or higher.

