9.10.2 Secondary Efficacy Endpoints

The secondary efficacy endpoints include the following variables.

1) Proportion of patients positive for virus titer and proportion of patients positive by RT-PCR at each time point

Defined as the percentage of patients whose virus titer is not < the lower limit of quantification among those assessed for virus titer, and the percentage of patients with detectable virus RNA among assessed by RT-PCR, respectively.

2) Change from baseline in virus titer and in the amount of virus (RT-PCR) at each time point

Defined as the change from baseline in virus titer and the change from baseline in the amount of virus RNA, respectively. Baseline is defined as the last value obtained before the initial dose.

3) AUC adjusted by baseline in virus titer and in the amount of virus RNA (RT-PCR)

Defined as AUC, where AUC is the area under the curve, of change from baseline in virus titer and AUC of change from baseline in the amount of virus RNA, respectively. AUC is calculated using the trapezoidal method.

4) Time to cessation of viral shedding by virus titer and by RT-PCR

Defined as the time between the initiation of the study treatment and first time when the virus titer is < the lower limit of quantification and the time between the initiation of the study treatment and first time when virus RNA by RT-PCR is < the lower limit of quantification, respectively.

5) Proportion of patients whose symptoms has been alleviated at each time point

Defined as the percentage of patients whose primary endpoints are improved after the initiation of the study treatment in the analysis population by each time point. 6) Time to alleviation of symptoms (cough, sore throat, headache, nasal congestion, feverishness or chills, muscle or joint pain, and fatigue)

Defined as the time between the initiation of the study treatment and the alleviation of influenza symptoms. The alleviation of influenza symptoms is defined as the time when all of 7 influenza symptoms have been assessed by the patient as 0 (None) or 1 (Mild) in the patient eDiary, for a duration of at least 21.5 hours (24 hours -10%).

7) Time to improvement in the 4 systemic symptoms (headache, feverishness or chills, muscle/joint pain, and fatigue)

Defined as the time between the initiation of the study treatment and the improvement in the 4 systemic symptoms. The assessment follows the criteria for the primary endpoint.

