9.10.3.2 Analyses of Secondary Endpoints

1) Proportion of patients positive for influenza virus titer and proportion of patients positive by RT-PCR at each time point

Only patients whose virus titer/RT-PCR predose at Visit 1 are \geq the lower limit of quantification will be included in the analyses. The summary table by each time

point will be made. The Mantel-Haenszel test at each time point will be used to compare the proportion of patients with positive virus titer/RT-PCR between S-033188 and oseltamivir/placebo with baseline symptom score ($\leq 14, \geq 15$), preexisting and worsened symptom (Yes, No), and region (Asia, North America/Europe, Southern Hemisphere) as stratification factors.

2) Change from baseline in virus titer and the amount of virus RNA (RT-PCR) at each time point

Only patients whose virus titer/RT-PCR predose at Visit 1 are \geq the lower limit of quantification will be included in the analyses. The van Elteren test will be used by each time point to compare the S-033188 with oseltamivir/placebo, where baseline symptom score ($\leq 14, \geq 15$), preexisting and worsened symptom (Yes, No), region (Asia, North America/Europe, Southern Hemisphere) will be included as stratification factors. Summary statistics will be calculated by time point and by treatment group.

3) AUC adjusted by baseline in virus titer and in the amount of virus RNA (RT-PCR)

Only patients whose virus titer/RT-PCR predose at Visit 1 are \geq the lower limit of quantification will be included in the analyses. The same statistical methods as 2) change from baseline in virus titer and the amount of virus RNA (RT-PCR) at each time point will be used. Summary statistics will be calculated by treatment group.

4) Time to cessation of viral shedding by virus titer and by RT-PCR

Only patients whose virus titer/RT-PCR predose at Visit 1 are \geq the lower limit of quantification will be included in the analyses. The same analyses as the primary endpoint will be performed.

5) Proportion of patients whose symptoms has been alleviated at each time point

The same analyses as 1) proportion of patients positive for influenza virus titer and proportion of patients positive by RT-PCR will be used.

6) Time to alleviation of symptoms

The same analyses as the primary endpoint will be performed.

 Time to improvement in the 4 systemic symptoms (headache, feverishness or chills, muscle/joint pain, and fatigue)

The same analyses as the primary endpoint will be performed.

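### Change and AUC of virus titer/RNA are tested without adjusting for the baseline value: the test is valid but inefficient

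*Protocol*

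**What the plan says.** Protocol Section 9.10.2 defines endpoint 2) as follows: "Defined as the change from baseline in virus titer and the change from baseline in the amount of virus RNA, respectively". It adds: "Baseline is defined as the last value obtained before the initial dose". Endpoint 3) is named as a baseline-adjusted AUC, but its definition reads: "Defined as AUC, where AUC is the area under the curve, of change from baseline in virus titer". Baseline is therefore subtracted and not used as a covariate.

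Section 9.10.3.2 item 2) fixes the test: "The van Elteren test will be used by each time point to compare the S-033188 with oseltamivir/placebo". The strata are baseline symptom score (two levels) together with the following: "preexisting and worsened symptom (Yes, No), region (Asia, North America/Europe, Southern Hemisphere) will be included as stratification factors". That makes 2 x 2 x 3 = 12 strata. Item 3) takes over the method: "The same statistical methods as 2) change from baseline in virus titer". In both items only patients at or above the lower limit of quantification before dosing are analysed, so every analysed patient has a measured baseline value. Section 9.1 sets the level: "All statistical tests will be performed at the 0.05 significance level using 2-sided tests".

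**The concern.** Subtracting a baseline is not the same as adjusting for it. A patient who starts high has further to fall, so change is negatively correlated with baseline whatever the treatment. A rank test on change then ranks patients partly by where they started, and that part carries no information about treatment.

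The quantification limit makes this stronger. Suppose values below the limit are set to a constant. The protocol does not say so; this is an assumption. The change of every patient who has cleared is then that constant minus baseline. With a limit of 0.7 log10, a patient who clears from 2.0 has a change of -1.3. That patient ranks as a poorer response than one still shedding at 4.0 from 6.0, whose change is -2.0.

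Comparing S-033188 with placebo and with oseltamivir on the secondary endpoints is a stated objective (Section 2.2). If the true difference is modest, which is more plausible against an active antiviral, a non-significant result could reflect the choice of test.

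**Working it through.** **The plan's own figures.** The only power figures concern the primary endpoint. With exponential times, censoring at 336 hours, two-sided 0.05 and 395 per arm, the generalized Wilcoxon test at medians of 114 and 150 hours has power 90.0%. The four rows of Table 9-1 come out at 22.2, 45.3, 71.5 and 90.2%, against the printed 22.3, 45.3, 71.5 and 90.2%. These reproduce. No figure for the virology endpoints exists to reproduce.

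**Analytic step (equal SDs, no floor).** Let sigma be the common SD and rho the baseline to post-baseline correlation.

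- Variance of change: 2 sigma²(1 - rho).
- Variance after baseline adjustment: sigma²(1 - rho²).
- Relative efficiency of the change score: sigma²(1 - rho²) / [2 sigma²(1 - rho)] = (1 + rho)/2.
- Correlation of change with baseline: -√((1 - rho)/2). This is -0.63 at rho 0.2 and -0.50 at rho 0.5.

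If the adjusted analysis has power P, the change-score analysis has power Φ[(1.96 + z_P)√((1 + rho)/2) - 1.96]. For P = 90% and rho = 0.2: (1.96 + 1.28) x √0.60 - 1.96 = 0.55, so the power is about 71%.

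| rho | Relative efficiency | Power if adjusted power is 90% | Power if adjusted power is 99% |
|---|---|---|---|
| 0 | 0.50 | 63.0% | 85.8% |
| 0.2 | 0.60 | 70.9% | 91.3% |
| 0.3 | 0.65 | 74.3% | 93.3% |
| 0.5 | 0.75 | 80.2% | 96.0% |
| 0.7 | 0.85 | 84.8% | 97.7% |

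**Simulation with a floor.** Only the 395 per arm, the 12-stratum layout and the 0.05 level come from the protocol, and 395 is an upper bound because patients below the limit predose drop out. Everything else is assumed: log10 baseline with mean 5.0 and SD 1.8, redrawn if below a limit of 0.7; post-dose SD 1.8 and mean 3.0 or 1.0 in the comparator; values below the limit set to 0.7; strata not prognostic. There were 400 runs per cell. The table shows power (%) for the planned van Elteren test, the same test with baseline tertile as an added stratum, and ANCOVA on the baseline value.

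| rho | Share at limit | Difference (log10) | Planned | + tertile | ANCOVA |
|---|---|---|---|---|---|
| 0.2 | 12% | 0.3 | 40.2 | 54.5 | 69.0 |
| 0.2 | 12% | 0.4 | 61.0 | 80.0 | 89.2 |
| 0.2 | 13% | 0.5 | 81.0 | 92.5 | 97.5 |
| 0.2 | 17% | 1.0 | 100 | 100 | 100 |
| 0.2 | 47% | 0.3 | 17.8 | 34.5 | 50.5 |
| 0.2 | 48% | 0.4 | 28.5 | 54.2 | 77.0 |
| 0.2 | 49% | 0.5 | 41.8 | 72.8 | 92.2 |
| 0.2 | 54% | 1.0 | 91.5 | 100 | 100 |
| 0.5 | 11% | 0.3 | 62.0 | 70.5 | 79.0 |
| 0.5 | 12% | 0.4 | 79.8 | 89.8 | 94.2 |
| 0.5 | 13% | 0.5 | 93.2 | 95.8 | 99.0 |
| 0.5 | 16% | 1.0 | 100 | 100 | 100 |
| 0.5 | 46% | 0.3 | 26.5 | 43.8 | 61.8 |
| 0.5 | 47% | 0.4 | 44.2 | 65.2 | 83.0 |
| 0.5 | 49% | 0.5 | 55.8 | 81.2 | 94.5 |
| 0.5 | 54% | 1.0 | 97.5 | 99.8 | 100 |

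At 0.3 to 0.5 log10 the gap between planned and ANCOVA runs from 99.0 - 93.2 = 5.8 to 92.2 - 41.8 = 50.4 points. At 1.0 log10 it runs from 0 to 100 - 91.5 = 8.5 points. The correlation of change with baseline is -0.55 to -0.84, stronger where more values sit at the limit. With no true difference, rejection is 3 to 7% for every method. The Monte Carlo standard error at 5% is √(0.05 x 0.95/400) = 1.1 points, so this is compatible with 5%.

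**Rank ANCOVA.** A separate run with the same sample size, SD and range of rho compared the planned test with a stratified rank ANCOVA at 0.4 log10. Power was 60 to 78% against 81 to 89% with about 12% at the limit, and 26 to 35% against 70 to 78% with about half. At 1.0 log10 the loss was between 0 and about 16 points.

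**AUC of change.** With assumed swabs on Days 2, 3, 5 and 9, SD 1.8, rho 0.2 or 0.5 and 600 runs per cell, the AUC correlated -0.82 to -0.87 with baseline. Planned against stratified rank ANCOVA power was 24 to 32% against 64 to 78% at 0.3 log10, 58 to 73% against 98 to 100% at 0.5, and 98 to 100% against 100% at 1.0. Null rejection was 3 to 7% for both.

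**The case against.** The strongest reply is that this is a choice between two valid tests, and that the size of the loss comes from inputs the protocol does not supply. It gives no SD, correlation, effect size or share at the limit for any virology endpoint. Its only relevant remark, in Section 3.2.1, describes the Phase 2 antiviral effect as fast and large, which points to the region where the planned test loses little, at least against placebo. This stands, and it limits what can be said about magnitude.

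Four stronger readings are tempting, and the documents do not support them:

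- **A reader might infer that much of the power is lost throughout.** That depends on rho, on the true difference and on the share of values at the limit, none of which is stated.
- **A reader might infer bias, or an inflated variance of the rank statistic.** Neither follows. Without ties, the null variance of a van Elteren statistic depends only on stratum and arm sizes. The loss arises because the statistic shifts less when there is a true effect. Chance imbalance at baseline is sampling variation that the test already covers.
- **A reader might infer that the antiviral case rests on these tests.** Items 1) and 4), proportion positive and time to cessation of shedding, also address it and do not rank change scores. The hierarchical error control in Sections 9.1 and 9.10.3.1.2 covers only the two comparisons on the primary endpoint.
- **A reader might infer that cleared patients are ranked on AUC by baseline alone.** The AUC also depends on when each patient clears, so the argument for item 2) does not carry over unchanged. The loss for AUC rests on the separate simulation.

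Leaving the matter to the SAP does not answer the point. The protocol names the test and the strata, and Section 9.1 says the SAP follows it and must explain departures.

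**Conclusion.** The concern holds as a question of efficiency. Items 2) and 3) leave out the baseline titer or RNA, and subtracting it does not replace adjustment. Type I error is intact. With equal SDs and no floor, the planned analysis has relative efficiency of about (1 + rho)/2, a loss of 15 to 50% for rho from 0.7 down to 0.

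Under the assumed inputs the power loss is substantial for differences of about 0.3 to 0.5 log10, above all when many values are at the limit. It is small near 1 log10 unless about half the values are there. The floor results also assume that values below the limit are set to a constant. These are secondary endpoints that did not drive the sample size, so the point is a worthwhile improvement and no threat to the trial's main conclusions.

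**What to change.** For items 2) and 3) of Section 9.10.3.2, replace the van Elteren test with a stratified rank ANCOVA, or an equivalent covariate-adjusted test. Use the predose Visit 1 titer (or RNA, for the RNA endpoint) as covariate and keep the three planned stratification factors. State how values below the quantification limit enter the change and the AUC.

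Keeping van Elteren and adding baseline tertile as a stratum is a weaker alternative. It turns 12 strata into 12 x 3 = 36 and, in the simulation, recovers only part of the loss.

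The cost is protocol or SAP wording and a few lines of code, settled before unblinding. No new data are needed, and ANCOVA is already planned for body temperature in item 11).

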4.2 Inclusion Criteria

Patients who fulfill all of the following criteria will be included in the study:

- 1. Patients or their legal guardians who provide written informed consent to participate in the study on a voluntary basis. For adolescent patients, informed consent/assent of voluntary participation should be obtained in accordance with local requirements (see Section 7.1).
- 2. Male or female patients ≥ 12 years at the time of signing the informed consent/assent form.
- 3. Patients with a duration of influenza symptoms confirmed by all of the following:
 - a. Fever \geq 38°C (axillary) during the predose examinations or within the 4 hours prior if antipyretics were taken
 - b. At least 1 each of the following general and respiratory symptoms associated with influenza (excluding those that are chronic and existed in the 30 days prior to the influenza episode) is present with a severity of moderate or greater:
 - i. General symptoms (headache, feverishness or chills, muscle or joint pain, or fatigue)
 - ii. Respiratory symptoms (cough, sore throat, or nasal congestion)
- 4. The time interval between the onset of symptoms and the predose examinations (Screening) is 48 hours or less. The onset of symptoms is defined as either:
 - a. Time of the first increase in body temperature (an increase of at least 1°C from normal body temperature)
 - b. Time when the patient experiences at least 1 new general or respiratory symptom
- 5. If a women of childbearing potential (WOCBP), agrees to use a highly effective method of contraception for 3 months after the first dose of S-033188 or oseltamivir (see Section 6.3.1 for approved contraceptive requirements).
- 6. Patients will be considered at high risk* of influenza complications due to the presence of at least 1 of the following inclusion criteria:

- a. Asthma or chronic lung disease (such as chronic obstructive pulmonary disease [COPD] or cystic fibrosis)
- b. Endocrine disorders (including diabetes mellitus)
- c. Residents of long-term care facilities (eg, nursing homes)
- d. Compromised immune system (including patients receiving corticosteroids not exceeding 20 mg of prednisolone or equivalent, and patients being treated for human immunodeficiency virus (HIV) infection with a CD4 count > 350 cells/mm³ within the last 6 months)

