5.4 Method of Assigning Patients to Treatment Groups

Each patient who is qualified for entry in the study will be randomized to S-033188, oseltamivir, or placebo in a ratio of 1:1:1. An interactive web response system (IWRS) will be used to assign patients to numbers for which treatment has already been randomly assigned. The randomization will use the stratified randomization method for balancing the following 4 factors: baseline symptom score ($\leq 14, \geq 15$), preexisting and worsened symptom (Yes, No: if a patient has at least 1 of 3 symptoms [namely cough, muscle or joint pain, or fatigue] that is preexisting and worsened, the patient will be assigned to the 'Yes' category , otherwise 'No'), region (Asia, North America/Europe, southern hemisphere), and weight (< 80 kg, \geq 80 kg). The registration center manager will prepare and complete the randomization procedures/processes.

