7.4.1.1 Body Temperature Measurement

With an electronic thermometer, the patient will self-measure axillary temperature. The sweat should be wiped off the measurement site in advance. The patient will measure and record in the patient eDiary, body temperature predose on Day 1, and then 4 times daily (morning, noon, evening, and bedtime) until Day 3 and twice daily (morning and evening) from Days 4 to 14. With Table 7-1 as a guide, the patient will measure body temperature when it is possible to do so. After the initiation of the study treatment, body temperature measurement will occur before taking acetaminophen or more than 4 hours after the last dose of acetaminophen.

The body temperature obtained at the study center prior to informed consent will be acceptable as an alternative to the predose value on Day 1 (provided that it is obtained on Day 1).

Assessment Period	Time Period of a Day	Time Window as a Guide
Assessment renou	Time reflot of a Day	Time window as a Guide
Days 1 to 3	Morning	- 9:59
	Noon	10:00 to 14:59
	Evening	15:00 to 19:59
	Bedtime	20:00 -
Days 4 to 14	Morning	- 11:59
	Evening	18:00 -

Table 7-1 Time Windows of Body Temperature Measurement as a Guide

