8) Time to improvement in the 3 respiratory symptoms (cough, nasal congestion, and sore throat)

Defined as the time between the initiation of the study treatment and the improvement in the 3 respiratory symptoms. The assessment follows the criteria for the primary endpoint.

9) Time to resolution of fever

Defined as the time between the initiation of the study treatment and the resolution of fever. The resolution of fever is defined as the time when the patient's self-measured temperature becomes $< 37^{\circ}$ C and is maintained at $< 37^{\circ}$ C for a duration of at least 12 hours.

10) Proportion of patients reporting normal temperature at each time point

Defined as the percentage of patients whose temperature resolves to $< 37^{\circ}$ C after the initiation of the study treatment in the analysis population.

11) Body temperature at each time point

Defined as measured axillary temperature.

12) Time to improvement of each influenza symptom

Defined as the time between the initiation of the study treatment and the alleviation of each influenza symptom. The alleviation of a symptom is defined as the time when the symptom is assessed as 0 (None) or 1 (Mild), for a duration of at least 21.5 hours (24 hours -10%).

13) Time to return to preinfluenza health status

Patients will be asked to record their preinfluenza health status between 0 (worst possible health) and 10 (normal health [for someone your age and your health condition]). Return to preinfluenza health status is defined as time from the initiation of the study treatment to time to the same number on scale for preinfluenza health status.

14) Requirement for systemic antibiotics for infections secondary to influenza infection

Defined as the percentage of patients treated with systemic antibiotics.

15) Incidence of influenza-related complications (hospitalization, death, sinusitis, bronchitis, otitis media, and radiologically confirmed pneumonia)

Defined as the percentage of patients in the analysis population who experience each influenza-related complication (hospitalization, death, sinusitis, otitis media, bronchitis, and radiologically-confirmed pneumonia) as an adverse event after the initiation of the study treatment. A specific complication eCRF with diagnostic criteria for the complications of sinusitis, otitis media, bronchitis, and pneumonia will be provided.

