9.10.3 Analyses of Efficacy Endpoints

9.10.3.1 Analyses of Primary Endpoint

9.10.3.1.1 Primary Analysis

The stratified generalized Wilcoxon test will be applied to the primary endpoint with some stratification factors, namely baseline symptom score ($\leq 14, \geq 15$), preexisting and worsened symptom (Yes, No), and region (Asia, North America/Europe, Southern Hemisphere) to evaluate the efficacy of S-033188 compared with placebo.

The same analysis in the PPS will be performed as a sensitivity analysis.

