8) Time to improvement in the 3 respiratory symptoms (cough, nasal congestion, and sore throat)

The same analyses as the primary endpoint will be performed.

9) Time to resolution of fever

The same analyses as the primary endpoint will be performed.

10) Proportion of patients reporting normal temperature at each time point

The summary table by each time point will be made. The Mantel-Haenszel test at each time point will be used to compare the proportion of resolution of fever between S-033188 and oseltamivir/placebo with baseline symptom score (≤ 14 , ≥ 15), preexisting and worsened symptom (Yes, No), and region (Asia, North America/Europe, Southern Hemisphere) as stratification factors.

11) Body temperature at each time point

The summary table by each time point will be made. The analysis of covariance (ANCOVA) will be used by each time point to compare body temperature between S-033188 and oseltamivir/placebo, where composite symptoms score at baseline, and preexisting and worsened symptom (Yes, No), and region (Asia, North America/Europe, Southern Hemisphere) will be used as covariates.

12) Time to improvement of each influenza symptom

The same analyses as the primary endpoint will be done. Patients whose symptoms at baseline are assessed as 0 (None), 1 (Mild), 2 (Moderate) but preexisting and not worsened, or 3 (severe) but preexisting and not worsened will be excluded from the analysis.

13) Time to return to preinfluenza health status

The same analyses as the primary endpoint will be performed.

14) Requirement for systemic antibiotics for infections secondary to influenza infection

A summary table will be created. The Fisher's exact test will be used to compare the percentage of patients who used systemic antibiotics for infections secondary to influenza infection between S-033188 and oseltamivir/placebo.

15) Incidence of influenza-related complications (hospitalization, death, sinusitis, bronchitis, otitis media, and radiologically-confirmed pneumonia)

A summary table will be created. Fisher's exact test will be used to compare the incidence between S-033188 and oseltamivir/placebo.

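### The ANCOVA of body temperature (secondary endpoint 11) leaves out predose temperature, which is already collected: the test is valid, but some precision is given up

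*Protocol*

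**What the plan says.** Section 9.10.2, item 11, gives the endpoint as the temperature itself: "Defined as measured axillary temperature". Section 9.10.3.2, item 11, analyses it by ANCOVA separately at each time point, "where composite symptoms score at baseline, and preexisting and worsened symptom (Yes, No), and region" being the covariates. No temperature term is listed.

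Section 7.4.1.1 schedules the missing variable. The patient records "body temperature predose on Day 1, and then 4 times daily (morning, noon, evening, and bedtime) until Day 3 and twice daily" from Day 4 to Day 14. A reading taken at the study centre on Day 1 before consent "will be acceptable as an alternative to the predose value on Day 1".

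Section 5.4 describes the allocation: "The randomization will use the stratified randomization method for balancing the following 4 factors". The four are baseline symptom score, preexisting and worsened symptom, region and weight.

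The item 11 covariates correspond to the stratification factors of the primary analysis in Section 9.10.3.1.1: "The stratified generalized Wilcoxon test will be applied to the primary endpoint with some stratification factors, namely baseline symptom score", then preexisting and worsened symptom, and region. One difference is that the primary analysis cuts the score at 14/15, whereas item 11 names the composite score without a cut.

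**The concern.** In an ANCOVA of a repeatedly measured quantity, the baseline value of that quantity is the natural covariate. Here the three variables that serve the symptom endpoint are used for temperature, and predose temperature is left out. Because the outcome is the raw value, baseline does not come in through a change score either. The other quantitative secondary endpoints do use their own baseline: items 2 and 3 analyse change from baseline in virus titer and RNA, and the area under that change.

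Bias is not at stake, since treatment is randomised. There are two consequences. The confidence interval for each temperature difference is wider than it need be. And if the arms happen to differ in predose temperature, the planned model does not correct for it beyond what the symptom score carries. Both should matter most at the early readings, where predose temperature is presumably most predictive; that is an assumption.

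**Working it through.** **The plan's own figures.** The protocol gives no power, SD or correlation for item 11. The nearest stated figure is the sample size in Section 9.2, which reproduces. With exponential times, medians of 114 and 150 hours, follow-up of 336 hours, two-sided 5% and 395 per arm, the generalized Wilcoxon test has 90.0% power. The Table 9-1 powers come out at 22.2, 45.3, 71.5 and 90.2%, against 22.3, 45.3, 71.5 and 90.2% stated. And 395/0.55 = 718.2, so 719 per arm and 3 × 719 = 2157 in total. The 395 per arm in the infected population (ITTI) is used below.

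**Precision.** Let ρ be the partial correlation of predose with later temperature in enrolled patients, given the three listed covariates. Then:

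- reduction in standard error (SE) from adding predose temperature = 1 − √(1 − ρ²)
- equivalent size per arm without the covariate = 395/(1 − ρ²)
- shift of the unadjusted difference for a 2-SE chance imbalance = 2ρ, in SE units of that difference

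| assumed ρ | SE reduction | equivalent n per arm | shift (SE) |
|---|---|---|---|
| 0.05 | 0.1% | 396 | 0.1 |
| 0.1 | 0.5% | 399 | 0.2 |
| 0.2 | 2.0% | 411 | 0.4 |
| 0.25 | 3.2% | 421 | 0.5 |
| 0.3 | 4.6% | 434 | 0.6 |
| 0.4 | 8.3% | 470 | 0.8 |
| 0.5 | 13.4% | 527 | 1.0 |

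In terms of power, a contrast with 90% power when adjusted would have 89.7%, 87.1% and 80.2% unadjusted at ρ = 0.1, 0.3 and 0.5.

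**Effect of a narrow predose range.** ρ = slope × (predose SD/outcome SD), with SDs taken after the existing covariates. Assume a predose SD of 0.4°C, an outcome SD of 0.8°C and slopes of 0.1 to 0.5. Then ρ runs from 0.1 × 0.4/0.8 = 0.05 to 0.5 × 0.4/0.8 = 0.25, and the SE reduction from 0.1% to 3.2%.

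In degrees, a 2-SE predose imbalance is 2 × 0.4 × √(2/395) = 0.057°C. Multiplied by the slope, it shifts the treatment difference by 0.006 to 0.028°C. An imbalance at least that large, in either direction, arises by chance in about 5% of trials.

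**Validity.** Two simulations were run with 395 per arm and the three existing covariates in both models.

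- 4000 runs at ρ = 0.1, 0.3, 0.5: type I error without predose temperature 5.2, 5.0, 5.0%; with it 5.3, 4.4, 4.9%. The SE ratio (with/without) was 0.996, 0.955, 0.867.
- 5000 runs at ρ = 0, 0.2, 0.3, 0.5, with predose values held at 38°C or above: without it 5.0, 4.8, 4.8, 5.4%; with it 5.0 to 5.2%. The SE ratio (without/with) was 1.00, 1.02, 1.05, 1.15.

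Both agree with the formula and with a nominal 5% test.

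**Number of readings.** The diary schedule allows at most 4 × 3 = 12 readings on Days 1 to 3 (fewer when dosing is late on Day 1) and 2 × 11 = 22 on Days 4 to 14, so 34 per comparison. If only the early readings gain, that is at most 12 of 34.

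**The case against.** The strongest reply is that this is a preference, not an error. The planned test is valid, nothing in the text contradicts itself, and the endpoint is one of 15 secondary endpoints. It has no stated power and lies outside the hierarchy, which Sections 9.1 and 9.10.3.1.2 confine to the two comparisons of the primary endpoint. All of that stands and is why the point is minor. It does not remove the point. The protocol fixes the covariate list, and Section 9.1 requires the SAP to give a reason for departing from it, so this is not a detail simply left open.

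Second, predose temperature is partly accounted for already. Feverishness or chills is one of the seven scored symptoms, the score is both a randomisation factor and a covariate, and entry requires fever of at least 38°C. This is fair. It lowers the partial correlation, which is why the low range is shown.

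Third, the predose reading may be a poor predictor if antipyretics affected it. Section 4.2 accepts fever "during the predose examinations or within the 4 hours prior if antipyretics were taken", and the spacing rule in Section 7.4.1.1 starts only with treatment: "After the initiation of the study treatment, body temperature measurement will occur before taking acetaminophen or more than 4 hours after". The synopsis words the same entry criterion differently, as a reading more than 4 hours after an antipyretic. Those two passages conflict and must be reconciled, so how far antipyretics would weaken the covariate cannot be settled from the text.

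Fourth, every size here is assumed, and in the narrow-range example a 2-SE imbalance moves the result by less than 0.03°C. That stands too. It limits the benefit without creating a reason to leave the covariate out.

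**Conclusion.** The concern holds, as a minor one. Item 11 names its covariates and omits the outcome's own baseline, which is collected and is not a randomisation factor. Type I error remains about 5%; the cost is precision and an uncorrected chance imbalance.

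The size rests on assumption, because the protocol gives no correlation, SD or slope. Partial correlations of 0.1 to 0.5 give an SE reduction of 0.5 to 13.4%, the equivalent of 399 to 527 per arm. The narrow-range example gives 0.1 to 3.2%. The documents do not show which range applies, though the entry criterion and the feverishness item both point towards the lower one. Confidence is high that the covariate is omitted, but does not extend to how much it would gain. The primary analysis, the comparison of the primary endpoint with oseltamivir, and the sample size are unaffected.

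**What to change.** In Section 9.10.3.2, item 11, add predose Day 1 axillary temperature as a continuous covariate, using the same-day study-centre reading where Section 7.4.1.1 permits it, and keep the three existing covariates.

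The cost is one degree of freedom per model and no new data. Two details need a sentence each: how patients with neither reading are handled, and that the study-centre value may stand in for the diary value, since Section 7.4.1.1 does not say at what body site it is measured. If the protocol is not amended, the SAP can make the change with its reason stated, before unblinding, as Section 9.1 provides.
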